9. SAFETY AND REPORTABLE EVENTS

9.1: Adverse Event Definition:

An adverse event is any symptom, sign, illness, or experience which develops or worsens during the course of the study, whether or not the event is considered related to study drug. It does not necessarily have a causal relationship with the vaccination. This can include exacerbations of underlying diseases or the development of an intercurrent illness. All subjects will be followed for the development of any adverse events throughout the course of the study.

9.2: Serious Adverse Event:

A serious adverse event is defined as any adverse medical experience that results in any of the following outcomes:

- Death;
- Is life-threatening;
- Requires inpatient hospitalization;
- Results in persistent or significant disability/incapacity;
- Requires medical or surgical intervention to prevent permanent impairment or damage.

9.3: Recording Adverse Events:

Study staff will assess adverse events by recording all voluntary complaints of the subject and by assessing the subject's clinical appearance. The subject will be questioned directly regarding the occurrence of any adverse experience since his/her last visit at each study visit. Solicited systemic AEs will include feverishness, malaise, fussiness, vomiting, and headache. Solicited local AEs will include URI symptoms or arm pain, tenderness, redness, or swelling.

All adverse events, whether observed by the Investigator or elicited from or volunteered by the subject, will be documented. Each adverse event description will include a brief description of the experience, the date of onset, the date of resolution, the duration and type of experience, the severity, likely relationship to study vaccine, any contributing factors, and any action taken.

9.4: Responsibilities for Reporting Serious Adverse Events:

The investigator will record all serious adverse experiences that occur during the study period in the case report forms and in an adverse event log. All unanticipated and serious events deemed possibly related to the study will be reported promptly to the RSRB.

10. RISK/BENEFIT ASSESSMENT

10.1: Potential Risks and Protection against Risks:

The risks and discomforts of this study include risks associated with the vaccine, risks associated with the study procedures (blood drawing, nasal wash and nasal swab), and possible loss of confidentiality.

While there are possible risks associated with administration of either LAIV or IIV (commonly including the development of a low grade fever or fussiness, the development a runny nose, headache, or sore throat from LAIV, or pain, redness, or swelling at the injection site from IIV), the administration of influenza vaccine to children is considered the standard of care. Thus, these risks are no greater than what would be experienced by children receiving the standard of care.

Blood draws may cause transient discomfort, which will be minimized using sucrose water in infants or distraction in older children. Bruising at the blood draw site also may occur, but can be prevented or

mitigated by applying direct pressure to the draw site for several minutes post blood draw. Development of infection is also possible, although unlikely, and will be prevented through the use of sterile technique (alcohol swabbing and the use of sterile equipment). The volume of blood per kg body weight being drawn is within a range considered safe. Nasal swabs are very safe and carry no significant risk in infants or children. Risks occasionally associated with nasal swabs include brief, minor irritation, and, rarely, transient bleeding. Nasal washes are also considered minimal risk, with the main risk being mild transient irritation, or, possibly transient bleeding. Long term side effects from any of these procedures are considered extremely unlikely.

Personal information on study subjects and their parents will also be collected to determine study eligibility and to account for possible confounding factors when performing data analysis. Research personnel will make every effort to keep this information confidential; however, a risk of participation is that the confidentiality of this information could be lost.

10.2: Potential Benefits to Subjects:

Although administration of influenza vaccines may result in the development of immunity that will prevent future influenza infection, this intervention is considered the standard of care and presumably would occur regardless of study participation. Infants presenting with influenza-like illness during influenza season will receive influenza testing as part of their evaluation, which has the potential to diagnose and potentially allow for the treatment of an active influenza infection. There are no other direct potential benefits to study participation.

10.3: Alternatives to Participation:

Subjects have the option to not participate in this study without any negative consequences.

11. CONFIDENTIALITY OF DATA AND INFORMATION STORAGE:

All data collected will be maintained in strict confidentiality according to accepted procedures and relevant HIPAA regulations. All demographic data, medical history, and identifiers will be stored in a coded manner in secured password protected files on computers, with hard-copy source documents secured in a locked area of the University of Rochester Medical Center. All subject samples will be identifiable only by a unique sample id and study number without any identifiers (i.e., name, date of birth, social security number or phone number). Identifying data that links the clinical and demographic data to clinical samples will be maintained by the investigators and kept in a secure location.

The study protocol, documentation, data and all other information generated will be held in strict confidence. No information concerning the study or the data will be released to any unauthorized third party. However, the clinical study site will permit access to all documents and records if required for inspection by regulatory authorities, including but not limited to the records for study subjects. Information that appears in publications will not include any data that can be directly linked to a specific individual.

All data will be stored until analyzed. It is anticipated that analysis of such complex data may continue beyond the proposed duration of the study. All aspects of confidentiality will continue to be maintained during this period, and all additional analyses will be covered by the original IRB approval, or a new IRB approval will be obtained. The data will be maintained indefinitely by one of the investigators, or an approved designee.

12. RESEARCH INFORMATION IN MEDICAL RECORDS:

Information or data generated as a result of the study will not be deposited into the subject's medical record. However, a flag will be added to the medical record for the duration of study participation to indicate that the subject is a study participant and will receive the subsequent year's influenza vaccine per the study protocol.

13. DATA ANALYSIS AND MONITORING

13.1: Sample Size Determination:

	d=0.3	d=0.35	d=0.4
n1=25, n2=25	0.738	0.858	0.934
n1=30, n2=30	0.815	0.915	0.968
n1=35, n2=35	0.871	0.95	0.985
n1=30, n2=10	0.517	0.646	0.761
n1=30, n2=15	0.64	0.772	0.871
n1=30, n2=20	0.721	0.844	0.924

The primary endpoint of this study is CD4 T cell responses. Based on a study of immune response in children and adults (62), the overall mean percentage of IFN γ + CD4 T cells in 5-9 year old children vaccinated with IIV or LAIV is around 0.1%, or -3 in log₁₀ scale. The standard deviation (STD) in log₁₀ scale is around 0.4. The geometric mean differences induced by vaccinations or between the two types of vaccination is around 0.3 in log₁₀ scale. The above table summarizes statistical power based on Student's two sample *t*-test. Assuming our responses are similar, recruiting n=30 subjects in each group will give us adequate power (0.815) for Aim 1. Because LAIV is an attenuated virus, it is reasonable to assume that the difference in CD4 T cell responses induced by IIV and natural influenza infection is larger (d=0.4), therefore recruiting

n=30 subjects in the IIV group and n=15 subjects in the infection group can achieve adequate power (0.871) for Aim 2. For Aim 3, assuming that within-group STD is 0.4 and between-group STD is just 0.2, the power is 0.851 if we recruit n=105 subjects divided them into four subgroups (n1=30, n2=30, n3=30, n4=15).

13.2: Planned Statistical Analysis:

We outline the statistical analysis strategies for the specific aims as follows. **Aim 1:** A cohort of n=60 healthy children will be recruited and divided into two groups with equal sample size (n=30); one group will be vaccinated with LAIV and the other with IIV. Their T cell and antibody responses will be measured at three time points: Baseline, day 10, and day 24 post-vaccination. We will apply Shapiro-Wilk's test to check the normality. If the data passes the normality test, two sample *t*-tests will be used to detect significant mean difference between the two groups at each time point. Otherwise, Wilcoxon rank-sum test will be used. Because multiple response variables are used in this analysis, the *p*-values will be adjusted by the Benjamini-Hochberg multiple testing procedure (80) to control the false discovery rate (FDR) at the level of 0.05. In addition to pairwise comparisons, the following linear mixed effect model will be used to analyze data collected from all time points:

$$y_{kit} = \alpha_k + \beta_k G(i) + \gamma_{kt} + \delta_{kit}. \quad (0.1)$$

Here y_{kit} represents the k th response variable measured from the i th subject at the t th time point; α_k is the overall mean value of y_{kit} ; $G(i)$ is a binary variable which equals 0 if the i th subject is vaccinated with LAIV and 1 otherwise; β_k is a linear coefficient that quantifies the magnitude of the group-effect; γ_{kt} is a random effect term that quantifies the time effects; and δ_{kit} represents independent measurement errors. Likelihood ratio test will be used to test $H_0: \beta_k = 0$ against $H_1: \beta_k \neq 0$. **Aim 2:** Two groups of infants will be recruited for this aim. The first group (n=30) will receive a prime-boost IIV series; the other group (n=15) consists of infants who are infected by influenza naturally. Multiple clinical endpoints will be recorded at 3 time points for both groups. We will apply two sample *t*-test (or Wilcoxon rank-sum test, if Shapiro-Wilks test rejects the assumption of normality) at each time point to detect significant group differences. In addition, we will apply a linear mixed effect model similar to Equation (1.1) to detect the overall group effect. The resulting *p*-values will be properly adjusted to control for FDR at a 0.05 level. **Aim 3:** All subjects (four subgroups; n=105) will be followed longitudinally for a year and then be revaccinated with IIV. CD4 T cell responses, antibody responses, and transcriptional profile (high-throughput RNA-seq) will be measured at three time points: prior to IIV re-vaccination, d10 and 24 days post re-vaccination. We will apply one-way ANOVA *F*-test (or Kruskal-Wallis test, if the normality assumption is rejected) to detect significant group differences at each time point. Post-hoc analysis based on Tukey's adjustment will be used to test for significant differences between groups. We will also apply a linear mixed effect model similar to Equation (1.1) to detect the overall group effect. For high-throughput transcriptional data, first we will apply suitable pre-processing techniques such as non-specific filtering (81), normalization (82) and batch-effect removing

(83). We then select differentially expressed genes at each time point by specialized procedures such as DEseq (84) and DEGseq (85). Benjamini-Hochberg procedure will be used to control FDR at a 0.05 level for all analyses.

13.3: Data and Safety Monitoring:

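### With unequal arms, Aims 2 and 3 should specify unequal-variance (Welch) tests: a cheap protection if the infection arm's SD differs from that of the vaccinated groups

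*Combined protocol and SAP*

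**What the plan says.** **Section 13.1 (sample size).** The power table uses the pooled form: "The above table summarizes statistical power based on Student's two sample" t-test. One SD serves every group: "The standard deviation (STD) in log₁₀ scale is around 0.4". The reference population is vaccinated and older than either cohort; the mean response "in 5-9 year old children vaccinated with IIV or LAIV is around 0.1"%. No infected group is mentioned. For Aim 2 the difference "induced by IIV and natural influenza infection is larger (d=0.4"), and "n=30 subjects in the IIV group and n=15 subjects in the infection group can achieve adequate power (0.871) for Aim 2".

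**Section 13.2 (analysis).** For Aim 2, "the other group (n=15) consists of infants who are infected by influenza naturally", and the two groups are compared at each time point by a two-sample t-test of unstated variance form, or by Wilcoxon rank-sum if Shapiro-Wilk rejects normality. A linear mixed model is added, and the p-"values will be properly adjusted to control for FDR at a 0.05 level". For Aim 3 the four subgroups are compared by a one-way ANOVA F-test (or "Kruskal-Wallis test, if the normality assumption is rejected"), with Tukey's adjustment post hoc.

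Neither section names Welch's test, any other unequal-variance method, or a variance check.

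**The concern.** The pooled t-test estimates one common variance. With equal arms it tolerates unequal SDs well. At 2:1 allocation it does not: the larger arm dominates the pooled variance, while the smaller arm contributes most of the uncertainty in the difference. If the smaller arm has the larger SD, the standard error is too small and false positives rise. If it has the smaller SD, the test is too strict.

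Three documented features make a larger SD in the infection arm plausible:

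- Its age range is 3-12 months, against 6-12 months in the IIV arm (section 3.2).
- Its day 10 and day 24 visits are timed from presentation with illness, which is only typically day 3-4 of illness. IIV infants are timed from a dated final dose (sections 2.2 and 5.1).
- Oseltamivir is optional and is arranged through each child's pediatrician (section 2.1).

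At stake is the reliability of the infection v IIV comparison, which addresses the second of the study's three hypotheses.

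**Working it through.** **Inputs.** From section 13.1: n = 30 and 15, difference 0.4 log10, common SD 0.4. Section 13.1 states no alpha; two-sided 0.05 is inferred because it reproduces all 18 cells of the power table to three decimals. The ratio r = infection SD / IIV SD is an assumption, shown over a range.

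**1. The plan's figure.** Pooled t-test, df = 30 + 15 − 2 = 43. Noncentrality = 0.4 / [0.4 × √(1/30 + 1/15)] = 1/√0.1 = 3.162. Two-sided power is 0.871, as stated. A one-sided test would give 0.929, and Welch's test with equal SDs gives 0.862, so the table is the two-sided pooled form.

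**2. Why the ratio matters.** Compare the variance that the pooled test uses on average with the true variance of the difference:

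- pooled: 0.16 × (29 + 14r²)/43 × (1/30 + 1/15)
- true: 0.16 × (1/30 + r²/15)

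At r = 1.5: pooled 0.16 × (60.5/43) × 0.1 = 0.0225; true 0.16 × (0.0333 + 0.1500) = 0.0293. The standard error is √(0.0225/0.0293) = 0.88 of what it should be. At r = 0.75: pooled 0.0137, true 0.0113, so the standard error is 1.10 times too large. With 30 v 30 (Aim 1) both expressions equal 0.16 × (1 + r²)/30, so the bias vanishes; simulated error there is only 0.051 to 0.053 for r from 1.5 to 3.

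**3. Size for one unadjusted Aim 2 test** (normal data, IIV SD 0.4, two-sided 0.05):

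| r (assumed) | Infection SD | Pooled type I error | Welch type I error | Welch power at 0.4 |
|---|---|---|---|---|
| 0.75 | 0.30 | 0.032 | about 0.050 | not tabulated |
| 1.0 | 0.40 | 0.050 | about 0.050 | 0.862 |
| 1.25 | 0.50 | 0.068 | about 0.050 | 0.73 |
| 1.5 | 0.60 | 0.085 | about 0.050 | 0.60 |
| 2 | 0.80 | 0.112 | about 0.050 | 0.41 |

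**4. Do the plan's own safeguards help?** Shapiro-Wilk examines shape, not spread. Simulating the whole rule on normal data (Shapiro-Wilk in each arm at 0.05, an assumption, then pooled t-test or Wilcoxon) gives 0.085 at r = 1.5 and 0.115 at r = 2, so nothing is recovered. The Benjamini-Hochberg step takes its input p-values as valid and does not correct them. The mixed model in section 13.2 has a single residual term, with no variance specific to group.

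**5. Aim 3** (30/30/30/15, with the group of 15 having r times the SD of the others). The F-test gives about 0.067, 0.084 and 0.124 at r = 1.25, 1.5 and 2. Welch's ANOVA stays near 0.05.

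**The case against.** Several stronger readings are tempting, and the documents do not support them.

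- **That the Aim 2 analysis is fixed as the pooled test.** Section 13.1 names Student's test for power only. Welch's test is also a two-sample t-test, so section 13.2 leaves the form open. What stands is that the only t-test form named anywhere is the pooled one. The Aim 3 F-test, by contrast, is named outright.
- **That the infection arm is more variable.** No section says so or gives its SD. The IIV arm has its own sources of spread: a dose interval of 28 (+14) days (section 2.3), trivalent or quadrivalent product (section 8.1), and boosters given at the research unit or the child's own practice (section 5.1). The 0.112 needs an infection SD of 0.8 log10, which nothing in the documents supports. At a ratio of 1.1 the error is only 0.057, and below 1 the test is conservative.
- **That a stated 5% level is breached.** The plan states an FDR of 0.05, not a per-test level. The figures above describe one unadjusted test, not the plan's realised FDR.
- **That Aim 3 is equally exposed.** In year 2 every child receives IIV at visit 4, and days 10 and 24 are counted from that dose (section 5.1). Illness timing and oseltamivir a year earlier are thinner reasons for unequal spread.
- **That 0.871 is wrong.** It is correct under equal SDs.

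These points limit the finding to a conditional one. They do not favour the equal-variance tests, because Welch's test holds its level whichever arm varies more.

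**Conclusion.** This is a worthwhile, inexpensive improvement, not a demonstrated error. As written, the plan allows equal-variance tests with unequal groups and has no protection if SDs differ. For Aim 2 the unadjusted pooled error would run from about 0.032 to about 0.112 over SD ratios 0.75 to 2, against about 0.050 for Welch. For Aim 3 the F-test would reach about 0.067 to 0.124 over ratios 1.25 to 2. These figures rest on assumed ratios, normal data, the full planned numbers, and a two-sided 0.05 level inferred from the power table. Aim 1 (30 v 30) is essentially unaffected.

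A separate consequence is that Aim 2 power depends on an SD borrowed from vaccinated 5-9 year olds. If infected infants vary more, power falls well below 0.871. That loss comes mainly from the larger SD, not from the choice of Welch's test.

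**What to change.** In section 13.2, specify Welch's unequal-variance t-test for Aim 2, and Welch's ANOVA with Games-Howell pairwise comparisons in place of the F-test and Tukey for Aim 3. Fix this before the data are examined, since the study is open-label and the variance form is currently open.

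In section 13.1, add Aim 2 power under Welch's test for a range of infection-arm SDs, stated as assumptions: 0.862 with equal SDs, then about 0.73, 0.60 and 0.41 at ratios 1.25, 1.5 and 2.

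The cost is a change of wording and about one point of Aim 2 power if SDs are in fact equal (0.871 − 0.862 = 0.009). If the Shapiro-Wilk switch to Wilcoxon is kept, a little inflation remains: about 0.054 at ratio 1.5 and 0.061 at ratio 2 for normal data, under the same assumed form of the rule.

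### The powers in Section 13.1 (0.815 and 0.871) are for a single unadjusted t-test, but Section 13.2 applies Benjamini-Hochberg across readouts, so for the planned per-readout test they are upper bounds

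*Combined protocol and SAP*

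**What the plan says.** Section 13.1 names a class of responses as the primary endpoint: "The primary endpoint of this study is CD4 T cell responses". It takes its inputs from one readout in an earlier study of older children, the percentage of IFN-γ+ CD4 T cells, with an SD of about 0.4 on the log10 scale. The planned difference is 0.3 for Aim 1 and 0.4 for Aim 2. "The above table summarizes statistical power based on" Student's two-sample t-test. No alpha, peptide pool, visit or multiplicity allowance is given. The section concludes that "recruiting n=30 subjects in each group will give us adequate power (0.815) for Aim 1" and that "n=30 subjects in the IIV group and n=15 subjects in the infection group can achieve adequate power (0.871) for Aim 2".

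Section 13.2 then describes the analysis. For Aim 1, "Their T cell and antibody responses will be measured at three time points: Baseline, day 10, and day 24 post-vaccination". The two-sample t-test (or the Wilcoxon test if normality fails) "will be used to detect significant mean difference between the two groups at each time point". "Because multiple response variables are used in this analysis", the p-values are adjusted by BH at a false discovery rate of 0.05. The same FDR level is required for Aim 2, and the last sentence of the section extends BH to every analysis. No CD4 readout, pool or visit is held outside the adjustment.

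**The concern.** A reader takes the power statement to describe the test that will be run. Here the sizing uses one test at an unadjusted level, whereas the analysis judges each readout at a BH cut-off that depends on how many tests share the family and how many of them are significant. If the two rules differ, the plan promises more for each readout than its own decision rule delivers. Aim 1 has little room, since 0.815 is only just above 0.80.

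The family itself is also undefined. Section 13.2 does not list the response variables or say whether the visits share one family. Antibody responses are measured too, and Section 5.3 allows the staining panel to change. The vaccines are given open label, so these choices are better fixed before data are seen.

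**Working it through.** **1. Reproduce the stated powers.** Inputs from Section 13.1: SD 0.4; difference 0.3 with 30 v 30 (Aim 1); difference 0.4 with 30 v 15 (Aim 2). The power of the pooled t-test comes from the noncentral t distribution with df = n1 + n2 − 2 and noncentrality (d/SD) / √(1/n1 + 1/n2).

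- Aim 1: 0.75 / √(1/30 + 1/30) = 0.75 / 0.2582 = 2.905, df 58, two-sided 0.05: power 0.8150.
- Aim 2: 1.0 / √(1/30 + 1/15) = 1.0 / 0.3162 = 3.162, df 43, two-sided 0.05: power 0.8710.

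All 18 table cells match in this way. One-sided 0.05 would give 0.890 and 0.929 and does not fit. The table is therefore arithmetically right, and it is unadjusted.

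**2. Direction under BH.** With m tests, BH rejects a readout only if its p-value is at or below (k/m) × 0.05, where k is the number of rejections and k ≤ m. The cut-off never exceeds 0.05, so every BH rejection is also an unadjusted rejection. At the same n, SD and difference, per-readout power cannot exceed 0.815 or 0.871. This needs no assumption about m or correlation. BH always rejects when p ≤ 0.05/m, so the floor is the power at that level: 0.726 / 0.796 for m = 2 and 0.531 / 0.614 for m = 8 (Aim 1 / Aim 2).

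**3. Hand check with two readouts** (for example IFN-γ to HA and to NP), independent and both real. A readout is declared if its own p ≤ 0.025, or if its p lies between 0.025 and 0.05 and the other p ≤ 0.05.

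- Aim 1: 0.726 + (0.815 − 0.726) × 0.815 ≈ 0.799.
- Aim 2: 0.796 + (0.871 − 0.796) × 0.871 ≈ 0.861.

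If only one of the two is real, simulation gives about 0.73 and 0.80.

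**4. Size with eight readouts at one visit.** The documents give no family size. Eight is an assumption: 2 peptide pools × 4 functional intracellular markers from Section 5.3. The share of real effects and the correlation are also assumed. Results are from simulation with equicorrelated normal readouts, correlation 0 to 0.8, BH at 0.05.

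| Truly different | Aim 1 (stated 0.815) | Aim 2 (stated 0.871) |
|---|---|---|
| 8 of 8 | 0.75–0.79 | 0.82–0.86 |
| 6 of 8 | 0.72–0.75 | 0.79–0.82 |
| 4 of 8 | 0.67–0.69 | 0.75–0.77 |
| 1 of 8 | 0.53–0.54 | about 0.62 |

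**5. Difference needed to regain the stated power** (8 readouts, correlation 0.5): about 0.32 (Aim 1) and 0.42 (Aim 2) if all are real; about 0.35 and 0.46 if half are.

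**6. Effect of grouping visits.** Aim 1, per-readout power at day 10, correlation 0.5 between readouts and between visits, no baseline difference:

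| Family | Day-24 difference | 8 real | 4 real |
|---|---|---|---|
| Per visit (8 tests) | not relevant | 0.76 | 0.67 |
| Days 10 and 24 (16 tests) | same as day 10 | 0.76 | 0.66 |
| Days 10 and 24 (16 tests) | half of day 10 | 0.68 | 0.58 |
| All three visits (24 tests) | same as day 10 | 0.70 | 0.60 |
| All three visits (24 tests) | half of day 10 | 0.61 | 0.52 |

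Pooling the two post-vaccination visits costs almost nothing if their differences are equal. The loss comes from adding null baseline tests or a weaker day-24 difference.

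**The case against.** Section 13.1 attaches its powers to aims, and an aim might be judged met if any readout differs. On that reading the figures need not be too high. With 8 readouts at one visit and correlation 0 to 0.8, the chance that at least one real readout is declared for Aim 1 is 0.83–1.00 (8 real), 0.80–0.99 (6 real) or 0.75–0.96 (4 real). The chance that a given real readout is declared at day 10 or day 24, with a family per visit and between-visit correlation 0.5, is 0.89 / 0.93 for Aim 1 / Aim 2 if all 8 are real and the day-24 difference equals that at day 10. It is 0.77 / 0.84 if the day-24 difference is half.

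That stands, but Section 13.1 does not power those events. Its table is for a single t-test, and the bound claimed here is limited to that test. It does not extend to the mixed model or to the Wilcoxon branch.

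It is also fair that the loss is small if most readouts differ: 0.02 to 0.06 for Aim 1 when all 8 do. Hypothesis 1 in Section 1.1, a larger and more polyfunctional response, points that way, and the sizing inputs are themselves approximate. The stated reason for adjustment, several response variables, also leans towards a family per visit without settling it. These points limit the size of the shortfall and leave its direction unchanged. FDR control is a suitable choice for a mechanistic study with many readouts and is not criticised here.

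**Conclusion.** The concern holds. The stated 0.815 and 0.871 are correct for one unadjusted two-sided 0.05 t-test, and they are upper bounds for the single-visit, per-readout t-test that Section 13.2 plans under BH. The direction is certain. The alpha level is inferred from exact reproduction of the table, since Section 13.1 does not state it.

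The size cannot be fixed from the documents, because family size, correlation and share of real effects are not given. Under the assumed settings it runs from a loss of a few points when nearly every readout differs to more than 25 points when one of eight does (0.815 − 0.53 = 0.285 for Aim 1; 0.871 − 0.62 = 0.251 for Aim 2). For Aim 1, even the favourable case of 8 real readouts falls below 0.80. Aim 2 stays above 0.80 in that case. The design stands; the power statement should be corrected.

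**What to change.** In Section 13.1, label 0.815 and 0.871 as unadjusted two-sided 0.05 power for one readout at one visit. Next to them, give per-readout power under BH at 0.05, with the assumed family size, correlation and share of true effects.

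In Section 13.2, list the response variables in the BH family, state whether the family is per visit or across visits, and state whether the Aim 1 baseline comparison belongs to it. Leaving baseline out avoids the dilution shown above.

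As an option, before data are seen, name one primary readout (one cytokine and one pool, or one pre-specified HA and NP combination) and one visit for each aim. Test it at two-sided 0.05 outside the FDR family and keep everything else under BH. For Aim 1, day 10 would fit, since Section 2.2 places the CD4 peak there. For Aim 2, 0.871 would then apply only with the IFN-γ inputs; an IL-2 readout, as hypothesis 2 suggests, needs its own SD and difference.

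The cost is a change of wording in two sections and a less favourable power sentence, with no extra children, samples or visits. Only the optional part narrows a primary objective that is worded as comprehensive.

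### The Aim 1 longitudinal model has no subject term and treats day 0 as an outcome, and the stated power of 0.815 is for one unadjusted test although the p-values will be Benjamini-Hochberg adjusted

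*Combined protocol and SAP*

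**What the plan says.** **Power.** Section 13.1 takes a standard deviation of 0.4 and a difference of 0.3 (both log10) from a published vaccine study, tabulates two-sample t-test power, and concludes that "recruiting n=30 subjects in each group will give us adequate power (0.815) for Aim 1". It states no significance level, primary visit or multiplicity allowance.

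**Per-visit tests.** Section 13.2, Aim 1: "Their T cell and antibody responses will be measured at three time points: Baseline, day 10, and day 24 post-vaccination". Two-sample t-tests "will be used to detect significant mean difference between the two groups at each time point", replaced by Wilcoxon rank-sum tests if Shapiro-Wilk rejects normality. No change score or baseline covariate is named. Because there are several responses, the p-values "will be adjusted by the Benjamini-Hochberg multiple testing procedure" at a false discovery rate of 0.05, and the last sentence of 13.2 extends this to every analysis. The family's members are not listed, and the plan does not say whether visits are pooled.

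**Mixed model.** Alongside these tests, model (0.1) is fitted to the data from all visits. Its group term "is a linear coefficient that quantifies the magnitude of the group-effect", its time term "is a random effect term that quantifies the time effects", and its residual "represents independent measurement errors". The group coefficient is tested by likelihood ratio. Aims 2 and 3 each use a model "similar to Equation (1.1) to detect the overall group effect"; only one equation is printed, labelled (0.1), so this must be the one meant.

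**The concern.** Each child contributes three samples, but nothing in model (0.1) links them: the random effect is indexed by response and time, not by child. The one analysis that uses all the data could therefore declare a vaccine difference too often, and the same structure is carried into Aims 2 and 3.

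Day 0 precedes vaccination, so no vaccine effect can be present there. One coefficient spanning all three visits averages a true zero with the post-vaccination effects and so no longer estimates the difference on which 13.1 is built.

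Finally, the sample size rests on the power of an unadjusted test, while the result will be judged after adjustment over a family that is not defined.

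**Working it through.** **Inputs.** From 13.1: difference 0.3, SD 0.4 (log10), 30 per group. The documents give no within-child correlation r, number of responses or share of responses truly affected, so these are assumed and ranges are shown.

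**1. The plan's figure.** Noncentrality = 0.3 / (0.4 × √(2/30)) = 2.905 on 58 df. At two-sided 0.05 the power is 0.815. All 18 cells of the table reproduce to three decimals on this basis; a one-sided test would give 0.890. The figure is arithmetically correct.

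**2. Type I error of model (0.1).** With equal correlation r between three visits, the variance of the group difference in child means is (2/n)σ²(1+2r)/3. The model takes it as (2/n)σ²/3. The inflation is 1+2r, so the actual size is about 2[1 − Φ(1.96/√(1+2r))].

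| r | 0.3 | 0.5 | 0.7 |
|---|---|---|---|
| Inflation 1+2r | 1.6 | 2.0 | 2.4 |
| Size by formula | 0.121 | 0.166 | 0.206 |
| Size simulated, model as written (40,000 runs) | 0.124 | 0.168 | 0.214 |
| Day 0 as covariate, still no subject term (8,000 runs) | 0.080 | 0.093 | 0.106 |
| Day 0 as covariate plus subject term, likelihood ratio | 0.056 | 0.053 | 0.059 |
| Same, F test with subject-level df | 0.049 | 0.048 | 0.051 |

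Moving day 0 to the right-hand side does not cure the inflation; the subject term is needed.

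**3. Dilution.** Effect 0.3 at both later visits: (0 + 0.3 + 0.3)/3 = 0.2. Effect at day 10 only: (0 + 0.3 + 0)/3 = 0.1. Adding only a subject term, with day 0 still an outcome, gives power of 0.74, 0.65 and 0.57 at r = 0.3, 0.5 and 0.7 for the first case.

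**4. Averaging days 10 and 24 instead, with day 0 as covariate.** The variance factor is (1+r)/2 − r² = 0.56, 0.50, 0.36, against (1+2r)/3 = 0.533, 0.667, 0.800 for the three-visit mean. Power depends on what happens at day 24:

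| Effect at day 10 / day 24 | r = 0.3 | 0.5 | 0.7 |
|---|---|---|---|
| 0.3 / 0.3 | 0.96 | 0.98 | 1.00 |
| 0.3 / 0.15 | 0.82 | 0.86 | 0.95 |
| 0.3 / 0 | 0.48 | 0.52 | 0.66 |

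Section 2.2 expects CD4 responses to be peaking at day 10 and contracting by day 24, so the first row is the favourable case.

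**5. Power under Benjamini-Hochberg.** If one test among m is non-null, the first-step threshold 0.05/m gives 0.670 (m = 3) and 0.571 (m = 6). Simulated day 10 power with 2 to 6 responses (20,000 runs; correlation 0.3 between responses, 0.5 between visits):

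| Responses affected | Family within a visit | Three visits pooled |
|---|---|---|
| All | 0.78–0.80 | 0.71–0.72 |
| Half | 0.69–0.73 | 0.61–0.64 |

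**6. ANCOVA at one visit.** Using SD × √(1−r²) and 57 df, single-test power is 0.815, 0.849, 0.909 and 0.979 at r = 0, 0.3, 0.5 and 0.7.

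**7. Wheeze default.** If a share w of the IIV arm had recent wheezing and differed by D at day 0, the carry-over into an unadjusted day 10 comparison is r × w × D. With r = 0.5 and w = 20%: 0.5 × 0.2 × 0.1 = 0.01 to 0.5 × 0.2 × 0.5 = 0.05 log10, for D of 0.1 to 0.5.

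**The case against.** Model (0.1) supplements the per-visit tests, and the sample size does not rest on it. That stands and limits the damage, but a supplementary test still needs its nominal error rate.

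Several stronger readings are tempting, and the documents do not support them:

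- *That the per-visit tests are wrong without baseline adjustment.* For randomised children they are valid; leaving out day 0 costs precision only.
- *That the wheeze rule biases Aim 1.* Children with recent wheezing do default to IIV (2.1, 8.3), but no baseline difference is documented, and 2.2 says such children respond equivalently to vaccine. That statement does not address day 0 levels. The assumed scenarios give 0.01 to 0.05 against an effect of 0.3.
- *That including day 0 always makes the estimate less precise.* From step 4, the three-visit mean has 0.56/0.533 = 1.05, 0.50/0.667 = 0.75 and 0.36/0.800 = 0.45 times the precision of the adjusted two-visit mean. The consistent defect is that it estimates a diluted quantity.
- *That power collapses under adjustment.* Benjamini-Hochberg is not Bonferroni. If every response differs and families are formed within a visit, the loss is only about 2 to 4 points. A figure of 0.36 arises with one real difference among 30 tests, but the 30-analyte multiplex panel serves a secondary objective; the primary readout is intracellular cytokine staining.

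The t-test in 13.1 is also the planned test; what the power figure leaves out is the adjustment.

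**Conclusion.** Two points stand.

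**The mixed model is wrong as written.** Any positive within-child correlation makes its group test anti-conservative. The size, about 0.12 to 0.21 against a nominal 0.05, rests on assumed equal correlations of 0.3 to 0.7 and 30 per group. The dilution of 0.3 to 0.2, or to 0.1 for a day-10-only effect, needs no assumption about correlation.

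**0.815 is single-test power.** It is correct for what it describes but is not the power of the adjusted Aim 1 analysis. The shortfall cannot be fixed from the documents: it runs from a few points if all responses differ within a visit to about 0.57 if one test in six is non-null.

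Baseline adjustment of the per-visit tests is recommended for precision, not as the correction of an error. The plan should be changed on the two points, but the per-visit comparisons survive as they are.

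**What to change.** 1. **Mixed model.** Use days 10 and 24 as outcomes, log10 day 0 as covariate, visit and group-by-visit as fixed effects, and a subject random effect or unstructured within-child covariance. Test the group contrast at each visit rather than relying on the average, preferably by an F test with subject-level degrees of freedom. Carry the subject term into the models for Aims 2 and 3.
2. **Per-visit comparison.** Compare arms at days 10 and 24 by ANCOVA on log10 day 0, and report baseline by arm descriptively, outside the tested family.
3. **Power and multiplicity.** Either label 0.815 as single-test power, define the Benjamini-Hochberg family and state power under it; or name one primary CD4 variable and visit tested at 0.05 outside the adjustment. The second option requires amending the sentence at the end of 13.2 that applies the adjustment to every analysis. The choice of variable is the sponsor's.
4. **Sensitivity.** Repeat Aim 1 in randomised children only.

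**Cost.** Wording only, with no new samples. ANCOVA uses one degree of freedom (0.8147 against 0.8150 at r = 0) and loses children without a day 0 sample: at 27 per group its power is 0.77, 0.81, 0.88 and 0.97 at r = 0, 0.3, 0.5 and 0.7. The randomised-only comparison is smaller (unadjusted power 0.77 at 30/24, and 0.721 at 30/20 in the protocol's own table), so it belongs as a sensitivity analysis.
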